Responsibilities for this study (Choose letters from list above and/or write in any others):

A B C E F H I

Conflict of Interest

1. Have all WSU employees, except student employees and graduate students, listed as personnel completed a disclosure of conflict of interest and time commitment for Wichita State University within the last 12 months? Yes No - submit a form via myWSU. For log on instructions: [Annual Conflict of Interest Reporting form](#)
2. Do any of the personnel (including students or their immediate family members) on the project have financial arrangements with the sponsoring company or the products or services being evaluated which may include consulting agreements, management responsibilities or equity holdings in the sponsoring company? Yes No N/A

If "Yes" please contact Compliance at [contact].

Project Information

1. Project Title: **Evaluation of Effects of Human-Animal Interaction on Physiological and Psychological Markers in Graduate Students**

2. Expected Completion Date: **04/30/2027**

3. Type of Project: Class Project Capstone Project Research

4. Type of Review Requested: Exempt

Expedited

Full Committee

5. Research Design: Experimental Quasi-Experimental Non-Experimental (e.g. descriptive, correlation)
 Qualitative Secondary Data/Collection/Analysis Program Evaluation or QI (STOP here, submit determination form)

6. Is the research funded? Yes No Plan to Submit for funding Have requested funding, awaiting award decision

Sponsor: **Kansas Health Foundation - Kansas Innovation Fund**

RTT Grant or Proposal # (if unsure ask your RTT contact):

KHF proposal #251231

Please submit a copy of the grant or statement of work from the contract.

6.1 If you have requested funding but do not receive it, will you still conduct the study? Yes No N/A

6.2 If the funding is from an industry contract, is there an agreement in place? Yes (fill in sponsor name above) No

In process, name of your RTT contact: N/A

7. List all locations where study activities will take place:

WSU Old Town Campus; [name]; specific rooms pending.

7.1. Will multiple institutions (other Universities, Hospitals, etc) participate in the study? Yes (complete #7.1a - 7.1c)
 No (proceed to #8)

7.1a. Please list all participating institutions:

7.1b. Has the IRB at the institution(s) listed above approved the study? Yes (please submit copy of approval letter)
 No, explain:

7.1c. Will the WSU PI oversee or coordinate the research being conducted at non-WSU sites? Yes No

If yes, Describe the PI's oversight plans, including how the PI will ensure adherence to the study protocol, obtain informed consent, secure and maintain IRB approval at the other sites, monitor adverse events or other unanticipated problems, and ensure general coordination of study conduct.

8. Please summarize the purpose of the proposed research using non-technical language that can be readily understood by someone outside the discipline:

The purpose of the study is to evaluate the effects of human-animal interaction on physiological and psychological markers in graduate students.

Graduate students face significant anxiety due to demanding coursework, long hours of studying, intense academic challenges, and the pressure to excel. Chronic stress in this population can contribute to elevated anxiety levels and measurable physiological changes, such as increased heart rate and blood pressure.

Human-animal interaction (HAI) and its effect on student stress, test anxiety, and physiological markers have been studied on college campuses, largely focusing on undergraduate students. However, research investigating the impact of HAI on graduate student stress, test anxiety, and physiological markers in high-stakes programs is limited. This study will evaluate the effectiveness of repeated HAI on graduate students' physiological markers and anxiety. The results of this study will assist participants, students outside this study, and the program administrators to appreciate the immense value of a full-time therapy dog on campus facilitating the human-animal bond in higher education.

9. Describe each procedure step-by-step, including the frequency, duration, and location of each procedure. A numbered or bulleted list of steps is helpful. *Submit a separate Word document if additional space is needed.*

Research Study:

*Location at [name], specific rooms TBD,

*Completed in the Fall 2025 semester,

*Frequency 1 time per week for 4 weeks,

*https://wichitastate.co1.qualtrics.com/jfe/preview/previewId/fe71f770-cbe3-414e-9174-865c7a4135db/SV_e9UIEaLk6Jdx0wu?Q_CHL=preview&Q_SurveyVersionID=current

Interventions:

Experimental: Human-animal interaction (HAI) - 15 minutes with therapy dog in training in groups of 2-3 participants, spending time doing what the participant wants to do (e.g., sitting quietly with the dog or playing with toys),

Control: General Health Education (GHE) - 15 minutes in groups of 2-3 participants being educated on anxiety-relieving techniques and concepts; handouts provided for the participants reference,

Sessions:

1. At session 1, each participant will read and sign the consent form. Each will complete the Generalized Anxiety Disorder-7 (GAD-7) anxiety assessment and the Academic Anxiety Scale (AAS); have blood pressure and heart rate taken with automated blood pressure cuff and O2 monitor respectively (pre- and post-interaction); complete a baseline salivatory cortisol test, complete a baseline pain pressure threshold measurement.

2. At sessions 2 & 3, each participant complete the AAS; have blood pressure and heart rate taken with automated blood pressure cuff and O2 monitor respectively (pre- and post-interaction); complete a salivatory cortisol test, complete a pain pressure threshold measurement.

3. At session 4, each participant will complete the GAD-7 and AAS; have blood pressure and heart rate taken with automated blood pressure cuff and O2 monitor respectively (pre- and post-interaction); complete a final salivatory cortisol test, complete a final pain pressure threshold measurement.

(Continued on supplemental attachment...)

10. Instruments:
 
 Standardized Tests  Questionnaire  Interview  Internet  Other (specify): See supplement...
	
11. Recorded by:
 
 Written Notes  Audiotape  Videotape  Photograph/film  Standard mail  Webcam/digital camera
	
12. Administered:
 
 In person (group)  In person (individual)  Telephone  Mail  E-Mail  Other (specify):
	
13. Findings used for....
 
 Publication  Dissertation, Thesis  Needs assessment  Evaluation  Results to be released to:


14. Data will include: (Check all variables, if no personal identifiers will be accessed please mark this box )
			

 Names of People  Mailing or Email Addresses  Phone or Fax Numbers  Age  Gender  Ethnicity  Marital Status  IP Address  Date of Birth  License, Certificate or Vehicle ID  Social Security Numbers  Medical Record Number  Admission/Discharge Date  Account Numbers
	
 Finger or voice print  Photographic image  Web URL  Biometric Identifiers  Income  Student ID#  Job Title  Names of employers  Types of employers  Other Information:
	
Blood pressure, heart rate, pain pressure thresholds, salivatory cortisol markers.
	

15. Will this study involve the use of existing data, documents, records, and pathological specimen?  Yes  No If "Yes", include a letter of authorization to access data if not publicly available.
			

16. Do you anticipate using any data from this study for other studies in the future?  Yes  No
			

If "Yes", explain:
			

17. Is this study similar or build upon a previous study approved by WSU IRB?  Yes - IRB# 5778 (similar to)  No
			

18. Do you intend to publish or present the study's findings?  Yes  No
			

Subject Selection
			

1. Number of Subjects or Records to be accessed: Not more than 30 participants
			

2. Age of Subjects: 20-35
			

3. Will all participants be fluent in English?  Yes  No
			

4. Vulnerable populations to be recruited (check all that apply):
			

 Children  Cognitively Impaired Persons  Prisoners  Minorities  Educationally or Economically disadvantaged
	
 N/A  Other –describe:
		

5. If vulnerable populations are targeted for the study, discuss the special protections being implemented to minimize risk of coercion or undue influence or  N/A.
			

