6.2 What are the primary exclusion criteria?

Students with diagnosed dog allergies; students with a fear of dogs; students diagnosed with mental health disorders; students with ongoing mental health treatment including (con't...)

7. Is Compensation Offered? Yes No If "Yes", describe amount, type (gift card, greenphire, etc) and when:

8. Describe the recruitment process, including any advertisements (flyers, emails, phone scripts, Strategic Communications Ads, etc.) to be used for this study. Include the flyer and text of the ads, emails, scripts as applicable in a separate document.

Participants will be recruited via an in-person presentation and explanation of the study by the research team.

Participants will be given the opportunity to sign up and navigate inclusion/exclusion criteria via a Qualtrics survey via a link sent through email from the PI.

https://wichitastate.co1.qualtrics.com/jfe/preview/previewId/fe71f770-cbe3-414e-9174-865c7a4135db/SV_e9UIEaLk6Jdx0wu?Q_CHL=preview&Q_SurveyVersionID=current

Risks/Benefit Information

1. Potential Risk Exposure: Physical (cognitive or motor) Psychological Economical Legal Social

2. Describe the nature and degree of the risks. (Do not say N/A - It cannot be assumed that there are no risks). Be sure all items listed are described in the informed consent document.

1. Minor physical risk from the human-animal interaction,
2. Minor physical risk from the salivatory cortisol test,
3. Minor physical risk for pain due to the pain pressure threshold testing/algometer.

3. Describe how risks and discomforts (physical, psychological, or social) will be minimized:

1. Risks due to animal interaction are minimized by having the animals trainer present, the animal having canine good citizen certification, and currently working through progression towards therapy dog certification.

2 & 3. Physical risks will be limited by training researchers and educating participants on research parameters.

2. All researchers will be properly trained how to obtain a salivatory cortisol test.
3. All researchers will be properly trained on the use of the pain pressure threshold algometer.

4. Please describe the benefits of the research to human subjects, if any, and of the benefits to human or scientific knowledge:

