...counseling or medications; students with known history of cardiac pathology and/or on cardiac medications.

List of included documentation:

- Co-investigator documentation
- Consent form
- Kansas Innovation Fund grant application
- Qualtrics email and Facebook announcement
- Non-acceptance email
- Generalized Anxiety Disorder (GAD-7)
- Academic Anxiety Scale (AAS)
- C-Barq questionnaire for therapy dog in training
- Algometer manual
- Algometer picture
- VitalTrack blood pressure cuff and pulse oximeter
- General Health Education (control group) documents:
 - 20 Benefits of Walking 30
 - How to deal with stress and anxiety
 - Sleep Hygiene
 - StressLess

GAD-7 Anxiety

Over the last two weeks , how often have you been bothered by the following problems?	Not at all	Several days	More than half the days	Nearly every day
1. Feeling nervous, anxious, or on edge	0	1	2	3
2. Not being able to stop or control worrying	0	1	2	3
3. Worrying too much about different things	0	1	2	3
4. Trouble relaxing	0	1	2	3
5. Being so restless that it is hard to sit still	0	1	2	3
6. Becoming easily annoyed or irritable	0	1	2	3
7. Feeling afraid, as if something awful might happen	0	1	2	3

Column totals _____ + _____ + _____ + _____ =

Total score _____

If you checked any problems, how difficult have they made it for you to do your work, take care of things at home, or get along with other people?

Not difficult at all

Somewhat difficult

Very difficult

Extremely difficult

Source: Primary Care Evaluation of Mental Disorders Patient Health Questionnaire (PRIME-MD-PHQ). The PHQ was developed by Drs. Robert L. Spitzer, Janet B.W. Williams, Kurt Kroenke, and colleagues. For research information, contact [name] at [contact]. PRIME-MD® is a trademark of Pfizer Inc. Copyright© 1999 Pfizer Inc. All rights reserved. Reproduced with permission

Scoring GAD-7 Anxiety Severity

This is calculated by assigning scores of 0, 1, 2, and 3 to the response categories, respectively, of "not at all," "several days," "more than half the days," and "nearly every day." GAD-7 total score for the seven items ranges from 0 to 21.

0–4: minimal anxiety

5–9: mild anxiety

10–14: moderate anxiety

15–21: severe anxiety

Academic Anxiety Scale

Please complete the following items using the four-point scale below.

1 = Not at all typical of me

2 = Somewhat typical of me

3 = Quite typical of me

4 = Very typical of me

1	I often worry that my best is not as good as expected in school.	1	2	3	4

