Use "to do" lists to help you focus on your most important tasks and take big projects one step at a time.

7. Practice giving back.

Volunteer your time or spend time helping a friend. Helping others helps you.

8. Be active every day.

Exercise can relieve mental and physical tension. Find something you enjoy and stick with it.

9. Give up the bad habits.

Too much alcohol, tobacco or caffeine can increase blood pressure. Cut back or quit to decrease anxiety.

10. Lean into things you can change.

Make time to learn a new skill, work toward a goal, or to love and help others.

Learn more at

[heart.org/HealthyForGood](https://www.heart.org/HealthyForGood).

© Copyright 2024 American Heart Association, Inc., a 501(c)(3) not-for-profit. All rights reserved.
Healthy for Good is a trademark of the AHA. Unauthorized use prohibited. WF497900 3/24

EAT SMART MOVE MORE BE WELL

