20 BENEFITS OF WALKING 30 MINUTES A DAY

01

REDUCES RISK
OF HEART
DISEASE

02

HELPS TO
MAINTAIN WEIGHT

03

REDUCES YOUR
STRESS LEVELS

04

INCREASES YOUR
ENERGY LEVELS

05

HELPS TO BOOST
YOUR MOOD

06

GETS THE
BLOOD
PUMPING

07

PREVENTS
OBESITY

08

CAN HELP TO
REDUCE
ANXIETY

09

INCREASES
FUNCTIONING
OF THE LUNGS

10

INCREASES THE
BODY'S ACCESS
TO VITAMIN D

11

REDUCES THE
RISK OF
CANCER

12

CAN IMPROVE
QUALITY OF
SLEEP

13

GIVES YOU TIME
TO PRACTICE
SELF CARE

14

IMPROVES
COORDINATION
AND BALANCE

15

IMPROVES
QUALITY OF
LIFE

16

REDUCES
CHANCE OF
DIABETES

17

WALKING CAN
SPARK
CREATIVITY

18

[figure not shown]
STRENGTHENS
BONES AND
MUSCLES

19

CAN IMPROVE
BLOOD
PRESSURE

20

CAN HELP TO
BOOST YOUR
IMMUNE SYSTEM

Sleep Hygiene

Recommendation 1: CHOOSE A STANDARD TIME TO WAKE UP

- Stick to it every day regardless of how much sleep you actually get
- Helps you develop a more stable sleep pattern
- You will train your brain to become sleepy at about the same time each evening

Recommendation 2: AVOID DOING THINGS YOU DO WHEN AWAKE

- Don't read, watch T.V., eat, study, use the phone, etc.
- Cut off the caffeine in the late morning/early afternoon
- If you avoid these activities while in bed, your bed will eventually become a place where it is easy to go to sleep and stay asleep.

Recommendation 3: NEVER STAY IN BED WHEN YOU'RE NOT SLEEPING

- Long periods of being awake in bed usually lead to frustration or worry about not sleeping
- These reactions make it more difficult to fall asleep.
- If you lie in bed awake for long periods, you are training your brain to be awake in bed
- You should get up if you find yourself awake for 20 minutes or more and you don't feel sleepy

Recommendation 4: SLOW THE BRAIN!

- Don't worry, mull over your problems, plan future events, or do other thinking
- If your mind seems to be racing or you can't seem to shut off your thoughts, get up and go to another room until you can return to bed without anything interrupting your sleep
- If disruptive thinking occurs frequently, you may find it helpful to routinely set aside a time each evening to do the thinking, problem-solving, and planning you need to do

[figure not shown]

Recommendation 5: AVOID DAYTIME NAPPING

- Sleeping during the day partially satisfies your sleep needs and will weaken your sleep drive at night

[figure not shown]
Recommendation 6: GO TO BED WHEN YOU ARE TIRED

- Keep a sleep log

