- Decide the amount of time to spend in bed, what time you should go to bed at night, and what time to get out of bed in the morning
- Be consistent

HOW TO DEAL WITH STRESS AND ANXIETY

MIND

Accept that you cannot control everything.

Put your stress in perspective: Is it really as bad as you think?

Do your best.

Instead of aiming for perfection, which isn't possible, be proud of however close you get.

Maintain a positive attitude.

Make an effort to replace negative thoughts with positive ones

Learn what triggers your anxiety.

Is it work, family, school, or something else you can identify? Write in a journal when you're feeling stressed or anxious, and look for a pattern.

HOW TO DEAL WITH STRESS AND ANXIETY

BODY

Limit alcohol and caffeine.

Alcohol and caffeine can aggravate anxiety and trigger panic attacks. Instead, drink water.

Eat well-balanced meals.

Do not skip any meals and always keep healthy, energy-boosting snacks on hand.

Get enough sleep.

When stressed, your body needs additional sleep and rest. It's important to get 8 hours of sleep per night!

Exercise daily.

Exercising can help you feel good and maintain your health

For more mental health information and resources visit:

www.mentalhealthamerica.net

HOW TO DEAL WITH STRESS AND ANXIETY

ACTION

Take deep breaths.

Inhale and exhale slowly throughout the day when you are feeling stressed.

10

Slowly count to 10.

Repeat, and count to 20 if necessary.

Give back to your community.

Volunteer or find another way to be active in your community, which creates a support network and gives you a break from everyday stress.

Take a time out.

Practice yoga, listen to music, meditate, get a massage, or learn relaxation techniques. Stepping back from problems helps clear your head.

Get help online.

If you are struggling with stress and anxiety in your life, consider taking a mental health screen. Screening is an anonymous, free, and private way to learn about your mental health. www.mhascreening.org

Talk to someone.

Tell friends and family you're feeling overwhelmed, and let them know how they can help you. Talk to a physician or therapist for professional help.

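### Do the take-home stress-management sheets, given only to the control arm, spoil the comparison of dog interaction with health education?

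*Protocol*

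**What the plan says.** Item 9 (Interventions) gives both arms 15 minutes in groups of 2-3, weekly for four weeks. HAI participants are with the dog, "spending time doing what the participant wants to do (e.g., sitting quietly with the dog or playing with toys". GHE participants are "being educated on anxiety-relieving techniques and concepts; handouts provided for the participants reference". The list of included documentation in the supplement files four sheets under GHE and marks them as control-group documents: walking, dealing with stress and anxiety, sleep hygiene, and StressLess.

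The sheets address daily habits:

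- StressLess, item 9: "Too much alcohol, tobacco or caffeine can increase blood pressure. Cut back or quit to decrease anxiety".
- Sleep Hygiene, recommendation 2: "Cut off the caffeine in the late morning/early afternoon".
- How to Deal with Stress and Anxiety: limit alcohol and caffeine (Body section). For those who are struggling, "consider taking a mental health screen"; and, after a line on telling friends and family, "Talk to a physician or therapist for professional help" (Action section).

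Exclusion criterion 6.2, continued in the supplement, rules out "students with ongoing mental health treatment including" "counseling or medications; students with known history of cardiac pathology and/or on cardiac medications".

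The session lists under Study Protocol place the questionnaires and the pre-interaction heart rate and blood pressure ahead of the 15-minute session. The GAD-7 is taken at sessions 1 and 4 and the Academic Anxiety Scale (AAS) at all four.

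**The concern.** The arms look matched on session length, group size and frequency, while one arm alone leaves with written instructions for the rest of the week. Blood pressure is an outcome, and one of the sheets itself links excess caffeine and alcohol to it. Counselling is kept out of both arms at entry, and then one arm is pointed towards professional help. Measures taken before the interaction at sessions 2 to 4 follow a week in which controls may have had the sheets and HAI participants had nothing comparable.

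If the sheets were an unintended extra, the arm difference in GAD-7, AAS and pre-interaction heart rate and blood pressure would mix two things: dog against education session, and sheets against no sheets. That could shrink a real benefit of HAI, and with at most 30 participants there is little room for it. Within-session changes in heart rate, blood pressure and pain threshold would be largely untouched.

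**Working it through.** The Protocol states no effect size, SD, power or alpha, so there is no figure of its own to reproduce. The question is settled mainly by setting the sections side by side.

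**1. What is being compared.** Item 9 names the handouts in the same sentence that defines GHE, and the documentation list files all four under GHE. They belong to the control condition. With random allocation, the mean difference between arms estimates the effect of HAI against education with handouts, and everything that follows from either package is part of that effect. To call the sheets a bias, one must replace this contrast with HAI against oral education alone. No section sets that target.

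**2. Counselling.** Criterion 6.2 governs who may enter. No section bars counselling during the study. The advice to see a physician or therapist is one general line, and the screen is suggested only to those who are struggling. Nothing here contradicts the criterion.

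**3. Caffeine and alcohol.** Three of the four sheets mention caffeine (StressLess, Sleep Hygiene, How to Deal) and two mention alcohol (StressLess, How to Deal). The blood-pressure statement concerns excess. Sleep Hygiene sets a time of day, not a lower intake. The documents give no participant's intake, so no change can be derived.

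**4. Which measures look back over the week.** The GAD-7 asks about the last two weeks but is not taken at sessions 2 and 3; only its session-4 score can cover time with the sheets. The AAS asks how typical each statement is of the respondent and sets no recall period.

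**5. Exposure arithmetic.**
- Longest possible time with the sheets before the session-4 questionnaires: 3 × 7 = 21 days. This assumes that all were handed out at session 1; the timing is not stated.
- GAD-7 window: 14 × 24 × 60 = 20,160 minutes. Session time in it: at most 2 × 15 = 30 minutes, and 30 / 20,160 = 0.15%. The same share holds for any weekly 15-minute intervention, with or without handouts, so it says nothing about bias.

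**6. Size in GAD-7 points.** Assume 15 controls (half of the cap of 30; the ratio is not stated).
- One control falling 5 points moves the mean by 5 / 15 = 0.33; five such controls move it by 25 / 15 = 1.67.
- A drop of one severity band can be a single point (5 to 4), which gives 1 / 15 = 0.07 for one control and 5 / 15 = 0.33 for five.

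The result follows wholly from the assumed number of responders and the assumed drop.

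**7. Power illustration.** Assume 15 per arm, two-sided alpha 0.05, SD 1 and the normal approximation: power = Φ(d × √(15/2) − 1.96).
- d = 1.0: Φ(2.739 − 1.960) = Φ(0.779) = 78%.
- d = 0.8 (controls improved by an assumed 0.2 SD): Φ(2.191 − 1.960) = Φ(0.231) = 59%.

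This shows that a trial of this size is sensitive to how effective its comparator is. It would hold equally if the 0.2 SD came from the teaching, and it does not show that the sheets produce it.

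**8. Would withholding the sheets equalise the arms?** Controls would still be taught anxiety-relief techniques at each session and could apply them all week. The between-session difference would remain, less whatever paper adds to remembered teaching, for which the documents give no figure.

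**The case for a change.** The strongest case is this. Item 8 of Project Information states the aim as the effectiveness of repeated HAI and names no comparator, and the findings are meant to persuade administrators of the value of a campus dog. A null result could then be read as the dog not working, when the contrast was with education plus self-management at home. Printed sheets can be separated from a taught session, and giving them to everyone after session 4 would cost almost nothing. No analysis can separate two components given only to the same arm, and the listed measures include no caffeine, alcohol or new counselling.

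Part of this stands. The contrast is with an active comparator, and any report should say so. The components of GHE cannot be separated afterwards, and the timing of the handouts is not stated in the text shown. But an active comparator is a legitimate choice, and not being able to take it apart is a limit on interpretation, not a bias in the comparison made. Removing the handouts would also weaken the control in the direction of the study's own expectation that HAI will do better. Reasonable statisticians would differ on that trade.

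**Conclusion.** The concern does not hold. The quoted facts and the arithmetic are right, but the sheets are a declared component of GHE, and the comparison of HAI with GHE is valid for the packages that Item 9 describes. No section contradicts another on this point. If the sheets work, the likely result is a smaller difference on between-session measures; that would not create a false claim in favour of HAI.

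The size of any such effect cannot be derived from the documents. The figures of 0.07 to 1.67 GAD-7 points and the fall in power from 78% to 59% illustrate assumptions only. The conclusion rests on two conditions: that participants are randomly allocated, which the supplement mentions only as a query, and that results are described as HAI compared with active education including handouts. When the sheets are given is a missing detail, not an error.
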